7.5.2 Clinical Laboratory Evaluation

Laboratory data consist of hematology, chemistry, and urinalysis laboratory tests. The National Cancer Institute's CTCAE version 4.0, will be used to categorize toxicity grade for the laboratory parameters. Normal ranges will be implemented to identify values that are outside the normal range.

Quantitative clinical laboratory variables from the hematology, chemistry, and urinalysis panels will be summarized using mean, standard deviation, minimum, maximum and median for each treatment group at each visit. These measurement values will be plotted as mean +/- SD plot. Additionally, a within-subject change will be calculated per visit as the post-baseline measurement minus the baseline measurement and summarized in the same way. For laboratory parameters that are gradable by the CTCAE, a shift table will be provided for each

For laboratory parameters that are gradable by the CTCAE, a shift table will be provided for each parameter to summarize baseline toxicity grade versus worst post-baseline toxicity grade during the treatment-emergent period by treatment line, separately. The number and percentage of subjects with at least one occurrence of grade 3 or grade 4 laboratory values in the treatment-emergent period will be summarized for each parameter and treatment group. The number and percentage of subjects with toxicity grade increase of two or more above baseline will also be summarized for each parameter and treatment group.

Each laboratory result will be classified as low (L), normal (N), or high (H) at each visit according to the laboratory supplied reference ranges. A high level overview shift table will be presented per parameter for each treatment group. Subjects who are normal at baseline and become low/high/low or high at any post-baseline time point will be summarized in the tables.

ISN/Protocol 9785-MA-3051

7.5.2.1 Liver function tests

The following potentially clinically significant criteria for liver tests – defined as ALP, Alanine Transaminase (ALT), total bilirubin, Aspartate Transaminase (AST) and their combination are defined. The subject's highest value during the investigational period will be used.

Parameter Criteria **ALT** > 3xULN> 5 x U L N**AST** > 3xULN> 5xULN**Total Bilirubin** > 2xULN ALP > 1.5xULN ALT and/or AST AND Total Bilirubin(*) (ALT and/or AST > 3xULN) and

total bilirubin > 2xULN

(*) Combination of values measured within same sample

The number and percentage of subjects with potentially clinically significant values in liver enzyme and total bilirubin tests during the investigational period will be presented by treatment arm. The same analysis will be provided dividing treatment lines.

7.5.3 **Vital Signs**

Vital signs (systolic blood pressure, diastolic blood pressure, and pulse rate) will be summarized using mean, standard deviation, minimum, maximum and median by treatment group and visit. These measurement values will be plotted as mean +/- SD plot. Additionally, a within-subject change will be calculated per visit as the post-baseline measurement minus the baseline measurement and summarized by treatment group and visit in the same way.

7.5.4 **ECOG** performance status

The number and percentage ECOG performance status will be presented by treatment arm. The same analysis will be provided dividing treatment lines.

7.5.5 **Electrocardiograms (ECGs)**

Not applicable.

7.5.6 **Pregnancies**

Not applicable.

7.5.7 **Other Safety-Related Observations**

Not applicable.

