3.1.3 Safety Objective

• To determine the safety of enzalutamide + ADT therapy as compared to flutamide + ADT therapy.

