4 SAMPLE SIZE

The number of evaluable subjects will be approximately 200 subjects (1st line AAT enzalutamide group: 100, 1st line AAT flutamide group: 100).

The sample size to evaluate the time to PSA progression with 1st line AAT (TTPP1), which is the primary endpoint of the study, was calculated in consideration of the following points:

• Median TTPP1 with enzalutamide: 10.5 months.

- Median TTPP1 with flutamide: 6 months.
 Values reported in the literature: 5 months according to [Okihara et al., 2007], 6.25 months according to [Narimoto et al., 2010].
- The ratio of randomization of 1st line AAT enzalutamide and flutamide groups is 1:1.

- Subject enrollment period is 12 months, and the observation period is 24 months from the enrollment of the last subject.
- Type I error of the two-sided test is 0.05, and power is 90%.
- A log-rank test with the TTPP1 parameters shown above requires 135 events. The
 necessary number of subjects calculated based on the required number of events is 74
 subjects per group.

Required number of events and necessary number of subjects above are calculated with the formulas below based on [Schoenfeld, 1983]. The codes in the formulas are defined as follows.

 M_t : Median TTPP1 in enzalutamide group

 M_c : Median TTPP1 in flutamide group

 t_a : Enrollment period

 t_f : Observation period from the last subject enrollment

 $Z_{1-\alpha}$: 1- α % point of standard normal distribution

 $Z_{1-\beta}$: 1-β% point of standard normal distribution

Hazard in enzalutamide group $(H_t) = \frac{\log_e 2}{M_t}$

Hazard in flutamide group $(H_c) = \frac{\log_e 2}{M_c}$

Hazard ratio for enzalutamide group/flutamide group (HR) = $\frac{H_t}{H_c}$

Required number of events $(N_d) = \frac{4 \times (Z_{1-\alpha} + Z_{1-\beta})^2}{(\log_e HR)^2}$ *The number after the decimal point will be rounded up to the nearest integer.

Incidence of events of enzalutamide group

$$(P_t) = 1 - \frac{1}{6} \left(\exp\left(-H_t \times t_f\right) + 4 \times \exp\left(-H_t \times \left(t_f + \frac{1}{2} \times t_a\right)\right) + \exp\left(-H_t \times \left(t_f + t_a\right)\right) \right)$$

Incidence of events of flutamide group

$$(P_c) = 1 - \frac{1}{6} \left(\exp(-H_c \times t_f) + 4 \times \exp\left(-H_c \times (t_f + \frac{1}{2} \times t_a)\right) + \exp\left(-H_c \times (t_f + t_a)\right) \right)$$

Incidence of events of both groups $(P) = \frac{1}{2} \times (P_t + P_c)$

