The treatment-emergent period will be defined as the period of time from the date of the first dose of study drug to 28 days after the date of the last dose of study drug, or 1 day prior to the date of initiation of cytotoxic chemotherapy for prostate cancer or an investigational agent treating prostate cancer, whichever occurs first. And 1st line treatment-emergent period is defined as the period of time from the date of the first dose of study drug in 1st line to 28 days after the date of the last dose of study drug in 1st line, or 1 day prior to the date of initiation of cytotoxic chemotherapy for prostate cancer or an investigational agent treating prostate cancer, whichever occurs first. Regarding 2nd line treatment-emergent period is applied same rule for 2nd line date.

• Baseline Value and Post-Baseline Value

Unless otherwise specified, the baseline value is defined as the last non-missing measurement prior to the randomization of study drug. When analysis be provided separately by treatment lines, baseline value for 2nd line AAT is defined as the last non-missing value measurement prior to the enrollment for 2nd line AAT of study drug.

Post-baseline value is defined as a measurement taken after the randomization of study drug. For Post-baseline value for 2nd line is defined as a measurement taken after enrollment during of study for 2nd line AAT.

Baseline value is defined as the last non-missing measurement prior to randomization (or register of 2nd line AAT) and post-baseline value is defined as a measurement taken after randomization for subjects who did not receive study drug. Change from baseline is defined as (post-baseline value - baseline value). Both date and time of drug administration and measurement should be considered when calculating baseline value. If time is not available, then date only should be used.

Treatment Group

Treatment group is defined as planned randomized treatment sequence which divide to initial enzalutamide 160 mg/day group or the initial flutamide 125 mg × 3 times daily (375 mg/day) group.

• Treatment Arm

Treatment arm is defined as administration drug group regardless 1st line or 2nd line treatment. That is enzalutamide plus ADT arm include subject who receive enzalutamide plus ADT at 1st line and 2nd line. Flutamide plus ADT include who receive flutamide plus ADT at 1st line and 2nd line.

• Treatment Line

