All analysis of safety will be presented by actual treatment group for SAF, unless specified otherwise. The last non-missing measurement prior to the first dose of study drug will be used as the baseline.

7.5.1 **Adverse Events**

The severity of all AEs is to be evaluated by the investigator based on the National Cancer Institute's CTCAE version 4.0. The coding dictionary for this study will be Medical Dictionary for Regulatory Activities (MedDRA) version 19.1. It will be used to summarize AEs by SOC and PT.

The safety analysis will be performed in the safety analysis set, and summarized by the time of assessment and by the treatment group that actually received the study drugs. The period of onset in the treatment period with the study drug is defined up to 28 days after the final treatment with the study drug, start date of cytocidal chemotherapy, or start date of new treatment for prostate cancer, whichever occurs first. Safety will be assessed by AEs, frequency of treatment discontinuation associated with AEs, and laboratory test value summary statistics. Descriptive statistics, and not inferential statistics, will be used.

The total number of AEs reported will be presented by treatment arm (i.e. enzalutamide v.s. flutamide) and overall total for the SAF. The same analysis will be provided dividing treatment lines. AEs which have occurred during 1st line AAT and 2nd line AAT will be included to analysis. In this 'event level' analyses, all AEs will be counted separately. The following categories will be presented:

- Number of AEs,
- Number of AEs leading to study drug discontinuation,
- Number of drug-related AEs,
- Number of drug-related AEs leading to study drug discontinuation,
- Number of grade 3 or higher AEs,
- Number of grade 3 or higher drug-related AEs,
- Number of serious adverse events (SAEs),

- Number of drug-related SAEs,
- Number of SAEs leading to study drug discontinuation,
- Number of drug-related SAEs leading to study drug discontinuation,
- Number of SAEs leading to death,
- Number of drug-related SAEs leading to death.

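### The pooled liver table and three laboratory tables span both lines of treatment, so they can attribute one drug's abnormal values to the other

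*SAP*

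**What the plan says.** The safety objective (SAP 3.1.3) is a comparison of the two drugs: "To determine the safety of enzalutamide + ADT therapy as compared to flutamide + ADT therapy". Under SAP 3.2, Group A takes enzalutamide and then flutamide, and Group B the reverse.

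SAP 7.1.2 defines three ways to classify data:
- Group: "Treatment group is defined as planned randomized treatment sequence".
- Arm, meaning the drug given in either line: "That is enzalutamide plus ADT arm include subject who receive enzalutamide plus ADT at 1st line and 2nd line". The flutamide arm is defined in the same way.
- Line: an analysis by line divides the data into first-line and second-line data.

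The outputs in question are these:
- **Liver thresholds (SAP 7.5.2.1).** ALT, AST, total bilirubin, ALP and their combination are presented by treatment arm, and the same analysis is repeated by line. The value used is set by one sentence: "The subject's highest value during the investigational period will be used".
- **Grade 3 or 4 (SAP 7.5.2).** The plan counts "subjects with at least one occurrence of grade 3 or grade 4 laboratory values in the treatment-emergent period will be summarized for each parameter". This table is broken down by treatment group. Rises of two or more grades are also by treatment group, and so is the low/normal/high shift at any post-baseline time. None of the three is split by line. The CTCAE worst-grade shift table in the same section is.
- **Baseline (SAP 7.5).** "The last non-missing measurement prior to the first dose of study drug will be used as the baseline". SAP 7.1.2 takes the first dose to be that of whichever study drug came first.

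**The concern.** Subjects who switch contribute laboratory values under both drugs. A worst-value table compares the drugs only if each value is credited to the drug being taken when it was measured. Adverse events have such a rule (SAP 6.2 assigns them through the treatment-emergent period). The worst laboratory values in these four tables do not.

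Liver toxicity is where this matters most. The flutamide package insert excerpt in Protocol 1.4.2 gives AST increased and ALT increased at 13.2% each, and serious liver disorder at 0.5%. If flutamide peaks also appear in the enzalutamide column, that column looks worse than the drug is and the contrast shrinks. A reader who takes the pooled table as the summary would be misled about both drugs.

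**Working it through.** **Reading the rules together**

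1. The SAP does not define the investigational period. The protocol's Definition of Key Study Terms runs it to the last assessment after study drug is completed. For a subject who switches, that covers both lines.
2. Such a subject is in both arms (SAP 7.1.2). One highest value per subject over that period, shown by arm, is therefore counted in both columns whichever drug produced it.
3. The unqualified treatment-emergent period in SAP 7.1.2 runs from the first dose of any study drug to 28 days after the last. The two-grade and low/normal/high tables name no line either. By randomized sequence, a Group A abnormality on second-line flutamide falls under initial enzalutamide, and the reverse holds for Group B.
4. The first-line treatment-emergent period runs 28 days past the last first-line dose and is not cut at the first second-line dose. Second line may start inside those 28 days, so the two windows can overlap.
5. On baseline, SAP 7.5 uses one value before any study drug. SAP 7.1.2 gives analyses by line a separate second-line baseline, and the protocol's definition of baseline uses Day 1 of each line for laboratory values. SAP 7.1.2 yields where something else is specified, and SAP 7.5 does specify something else. This affects the two-grade table and the shift tables. It does not affect 7.5.2.1, whose criteria are multiples of the upper limit of normal.

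**Size (illustration)**

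The plan gives no figure on this point to reproduce. Let f be the share of subjects over a threshold on flutamide, e the share on enzalutamide, and s the share of each group that switches. All are assumed, with the two drugs' signals independent of each other and of switching.

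- Switcher, whole period: X = 1 − (1 − f)(1 − e)
- Group A = (1 − s)e + sX; Group B = (1 − s)f + sX
- Enzalutamide arm = (A + sX)/(1 + s); flutamide arm = (B + sX)/(1 + s)

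For f = 10%, e = 1%, s = 80%:
- X = 1 − 0.90 × 0.99 = 0.109
- A = 0.2 × 0.01 + 0.8 × 0.109 = 0.0892
- B = 0.2 × 0.10 + 0.8 × 0.109 = 0.1072
- Enzalutamide arm = (0.0892 + 0.0872)/1.8 = 0.098
- Flutamide arm = (0.1072 + 0.0872)/1.8 = 0.108

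| f, e, s | Flutamide vs enzalutamide, by arm | Group B vs Group A |
|---|---|---|
| 10%, 1%, 80% | 10.8% vs 9.8% | 10.7% vs 8.9% |
| 5%, 1%, 50% | 5.6% vs 4.3% | 5.5% vs 3.5% |
| 13.2%, 2%, 25% | 13.9% vs 7.2% | 13.6% vs 5.2% |
| 13.2%, 2%, 50% | 14.4% vs 10.6% | 14.1% vs 8.5% |
| 13.2%, 2%, 75% | 14.7% vs 13.1% | 14.5% vs 11.7% |
| 13.2%, 2%, 90% | 14.8% vs 14.3% | 14.8% vs 13.6% |

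Subtracting the formulas gives a by-group gap of (1 − s)(f − e) and a by-arm gap of (1 − s)(f − e)/(1 + s). In the first row, 0.2 × 9 = 1.8 points by group and 1.8/1.8 = 1.0 point by arm, against a true 9. In the second row, 0.5 × 4 = 2.0 and 2.0/1.5 = 1.3 points, against a true 4. In the last four rows the true 11.2 points fall to between 8.4 and 1.1 by group. The 13.2% is any AST or ALT increase, not the rate above 3 × ULN. A table restricted to first line would show f against e unchanged.

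**The case against.** The strongest reply is that the SAP plainly knows about the switch. It defines group, arm and line for that reason. It repeats the liver analysis by line, and by-line analysis means divided data, so the highest first-line value is a first-line value. The CTCAE shift table is by line. Adverse events, which include clinically significant laboratory abnormalities (Protocol 5.5.1), are assigned to a drug period and shown by arm and by line. All of this stands. A reader might infer that the plan ignores the crossover or leaves the safety objective unanswered. The documents do not support that: the first-line liver table is a randomized comparison made before any switch, and it is already planned.

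Second, arm means the drug administered, and SAP 7.5 promises presentation by actual treatment, so a programmer might restrict each peak to the time on that drug. That is possible, but the sentence in 7.5.2.1 does not say so, and presentation by actual treatment conflicts with the definition of group as the planned sequence. The separate table and data specifications that the SAP mentions are not among the documents and could settle it.

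Third, Protocol 3.4 bars a shift to flutamide when the latest AST or ALT exceeds the upper limit of normal. That limits carry-over of raised values into Group A's second line and weakens the independence assumption. It does not touch flutamide abnormalities that arise after the switch. In the other direction, Protocol 6.1 allows subjects who stopped first-line flutamide for liver disorder to move to second line, taking their flutamide peak into the enzalutamide arm.

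Fourth, a reader might infer from SAP 7.5 that first-line changes are certainly counted again in second line. SAP 7.1.2 already has a second-line baseline, so what can be shown is a conflict between two rules.

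**Conclusion.** The fault is real in four descriptive tables: the pooled by-arm liver table, and the grade 3 or 4, two-grade and low/normal/high tables by group. Followed as written, they can attribute one drug's values to the other. The pull is towards equality and grows with the share who switch. In the two main illustrations, a true gap of 9 or 4 points becomes 1.0 or 1.3 points by arm and 1.8 or 2.0 points by group.

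Those sizes rest on assumed rates, an assumed switching share equal in both groups, and independence. The documents give neither an enzalutamide rate for these thresholds nor a switching share. The direction needs only that flutamide has the higher rate and that some subjects switch. Because the by-line liver, by-line CTCAE shift and adverse event tables are planned, the safety objective is still addressed. The baseline conflict is a separate inconsistency to resolve. Severity: should-fix.

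**What to change.** - **SAP 7.5.2.1:** replace the value rule with the subject's highest value within the treatment-emergent period of each line, ended for this analysis at the first dose of the next line, and assign it to the drug taken in that line. The by-arm table then combines correctly attributed values.
- **SAP 7.5.2:** produce the grade 3 or 4, two-grade and low/normal/high tables by drug within line, and name first line as the randomized comparison.
- **SAP 7.5:** state that second-line changes use the second-line baseline already defined in SAP 7.1.2.

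The cost is SAP wording and table programming. Laboratory values and dosing dates are already collected for each line, so no new data are needed.

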7.6 Analysis of PK

Not applicable.

7.7 Analysis of PD

Not applicable.

7.8 Subgroups of Interest

Primary efficacy endpoint, TTPP2, PSA Response Rate to 1st Line AAT, PSA Response Rate to 1st Line AAT at Week 13 and rPFS, analyses will be repeated by the subgroups defined on the basis of the categorized variables listed below:

- Baseline ECOG performance status (0 vs \geq 1)
- Age category (<75 and ≥ 75 years), (at or below median vs above median)
- Total Gleason score (≤ 7 and ≥ 8) at diagnosis
- Type of progression (PSA progression only vs radiographic progression with or without PSA progression) at study entry
- Baseline PSA value (at or below median vs above median)
- PSA value at initial diagnosis (at or below median vs above median)
- Baseline LDH value (at or below median vs above median)
- Baseline hemoglobin value (at or below median vs above median)
- Baseline ALP value (at or below median vs above median)
- Treatment duration of bicalutamide (at or below 12 months vs above 12 months), (at or below median vs above median)
- PSA nadir value on CAB therapy ($\leq 4 \text{ng/mL vs} > 4 \text{ng/mL}$), ($\leq 0.2 \text{ng/mL vs} > 0.2 \text{ng/mL}$)
- PSA response rate to 1st line AAT at Week 13 (below 50% vs at or above 50% reduction from baseline), (below 90% vs at or above 90% reduction from baseline) *except for the analysis of PSA Response Rate to 1st Line AAT at Week 13.
- Baseline NLR value (at or below median vs above median)
- Baseline testosterone value (at or below median vs above median)
- Treatment duration of first line hormonal therapy (at or below 12 months vs above 12 months), (at or below median vs above median)
- Disease stages (M0/N0 vs M0/N1 vs M1)
- PSA doubling time (at or below median vs above median)

Also, selected safety variables (treatment emergent adverse events) will be summarized by the treatment group for the subgroups defined on the basis of the categorized variables listed below:

- Baseline ECOG performance status (0 vs \geq 1)
- Age category (<75 and ≥ 75 years), (at or below median vs above median)

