7.1 Sample Size

The number of evaluable subjects will be approximately 200 subjects (1st line AAT enzalutamide group: 100, 1st line AAT flutamide group: 100).

The sample size to evaluate the time to PSA progression with 1st line AAT (TTPP1), which is the primary endpoint of the study, was calculated in consideration of the following points:

- Median TTPP1 with enzalutamide: 10.5 months.
- Median TTPP1 with flutamide: 6 months. Values reported in the literature: 5 months according to [Okihara et al., 2007], 6.25 months according to [Narimoto et al., 2010].
- The ratio of randomization of 1st line AAT enzalutamide and flutamide groups is 1:1.
- Subject enrollment period is 12 months, and the observation period is 24 months from the enrollment of the last subject.
- Type I error of the two-sided test is 0.05, and power is 90%.
- A log-rank test with the TTPP1 parameters shown above requires 135 events. The necessary number of subjects calculated based on the required number of events is 74 subjects per group.

Required number of events and necessary number of subjects above are calculated with the formulas below based on [Schoenfeld, 1983]. The codes in the formulas are defined as follows.

 M_t : Median TTPP1 in enzalutamide group

 M_c : Median TTPP1 in flutamide group

 t_a : Enrollment period

 t_f : Observation period from the last subject enrollment

 $Z_{1-\alpha}$: 1- α % point of standard normal distribution

 $Z_{1-\beta}$: 1- β % point of standard normal distribution

[figure not shown]
Hazard in enzalutamide group $(H_t) = \frac{\log_e 2}{M_t}$ Hazard in flutamide group $(H_c) = \frac{\log_e 2}{M_c}$ Hazard ratio for enzalutamide group/flutamide group $(HR) = \frac{H_t}{H_c}$ Required number of events $(N_d) = \frac{4 \times (Z_{1-\alpha} + Z_{1-\beta})^2}{(\log_e HR)^2}$ *The number after the decimal point will be rounded up to the nearest integer. Incidence of events of enzalutamide group $(P_t) = 1 - \frac{1}{6} \left(\exp(-H_t \times t_f) + 4 \times \exp\left(-H_t \times (t_f + \frac{1}{2} \times t_a)\right) + \exp\left(-H_t \times (t_f + t_a)\right) \right)$ Incidence of events of flutamide group

$$(P_c) = 1 - \frac{1}{6} \left(\exp\left(-H_c \times t_f\right) + 4 \times \exp\left(-H_c \times (t_f + \frac{1}{2} \times t_a)\right) + \exp\left(-H_c \times (t_f + t_a)\right) \right)$$

Incidence of events of both groups $(P) = \frac{1}{2} \times (P_t + P_c)$

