7.4.1.3 Subgroup Analysis

For the primary and secondary analyses on the primary endpoint, TTPP1, subgroup analyses will be performed. Subgroup setting is specified by the SAP.

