3.1.4 Exploratory Objectives

- To evaluate time to PSA progression with 2nd line AAT (2nd time to PSA progression [2nd TTPP]).
- To evaluate PSA response rate to 2nd line AAT.
- To determine the benefit of enzalutamide + ADT therapy as compared to flutamide + ADT therapy as assessed by metastasis-free survival (MFS).

To evaluate Quality of Life (QOL) on 1st line AAT and 2nd line AAT using Functional Assessment of Cancer Therapy—Prostate (FACT-P) and European Quality of Life 5-Dimension-5 Level instruments (EO-5D-5L).

- To evaluate Brief Pain Inventory-Short Form (BPI-SF) with 1st line AAT and 2nd line AAT.
- To evaluate Brief Fatigue Inventory (BFI) with 1st line AAT and 2nd line AAT.
- To determine the benefit of enzalutamide + ADT therapy as compared to flutamide + ADT therapy as assessed by objective response rate (ORR) in soft tissue with 1st line AAT based on the best overall response in Response Evaluation Criteria in Solid Tumors (RECIST) guidelines.
- To evaluate the efficacy in subgroups according to disease-related patient demographics.

3.2 **Study Design**

This is a randomized, open-label, comparative study on enzalutamide and flutamide.

Patients with M0 or M1 castration-resistant prostatic neoplasm that relapsed during combined androgen blockade (CAB) therapy with bicalutamide will be randomized to Group A or B. Dynamic allocation will be performed with minimization with biased coin technique. The following stages (M0/N0, M0/N1, or M1) will be used as allocation factors.

- M0/N0: No distant metastasis, and no lymph node metastasis
- M0/N1: Without distant metastasis, but with metastasis in lymph nodes distal to the aortic bifurcation
- M1: With distant metastasis (including metastasis in lymph nodes proximal to the aortic bifurcation)

For subjects in Group A, enzalutamide is administered as the 1st line AAT. After the confirmation of PSA progression, medication is changed from enzalutamide to flutamide as the 2nd line AAT. For subjects in Group B, flutamide is administered as the 1st line AAT. After the confirmation of PSA progression, medication is changed from flutamide to enzalutamide as the 2nd line AAT. The treatment period with each drug should not be more than 2 years from the enrollment of the last subjects.

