7 STATISTICAL METHODOLOGY

7.1 General Considerations

7.1.1 General Principles

For continuous variables, descriptive statistics will include the number of subjects (n), mean, standard deviation, median, minimum and maximum. When needed, the use of other percentiles (e.g.10%, 25%, 75% and 90%) will be mentioned in the relevant section. Frequencies and percentages will be displayed for categorical data. A missing category will be added to categorical variables where data is missing.

Summaries based on ITT (e.g. disposition, baseline and efficacy data) will be presented by planned treatment group, unless specifically stated otherwise. Safety analysis and other summaries based on SAF will be presented by actual treatment received.

All statistical comparisons will be made using two sided tests at the α =0.05 significance level unless specifically stated otherwise. All null hypotheses will be of no treatment difference, all alternative hypotheses will be two-sided, unless specifically stated otherwise.

All data processing, summarization, and analyses will be performed using SAS® Version 9.4 or higher on Windows. Specifications for table, figures, and data listing formats can be found in the TLF specifications for this study.

The Age (Derived) variable from EDC will be used for analysis. If date of birth is incomplete, the variable Age from EDC will be used for analysis.

Year will be calculated as (days/365.25) rounded up to 1 significant digit.

Month will be calculated as (days/30.4375) rounded up to 1 significant digit.

Time to event or duration of event endpoints will be based on the actual date rather than Visit Day.

For the definition of subgroups of interest please refer to section 7.8.

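### The subgroup plan repeats 0.05-level tests inside 20 baseline splits, but no planned analysis compares the treatment effect between subgroup levels (minor, exploratory)

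*SAP*

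**What the plan says.** The objective is listed as exploratory in SAP 3.1.4: "To evaluate the efficacy in subgroups according to disease-related patient demographics". Protocol 7.4.1.3 reads: "For the primary and secondary analyses on the primary endpoint, TTPP1, subgroup analyses will be performed. Subgroup setting is specified by the SAP". SAP 7.8 then states that the "analyses will be repeated by the subgroups defined on the basis of the categorized variables listed below", and applies this to TTPP1, TTPP2, PSA response to 1st line AAT, PSA response at Week 13, and rPFS.

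What is repeated in each level follows from the main analysis sections:

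- **TTPP1** (SAP 7.4.1): stratified log-rank test, Cox hazard ratio with 95% CI, Kaplan–Meier estimates.
- **rPFS** (SAP 7.4.2.7): the TTPP1 method, in subjects with distant metastasis at baseline.
- **Both PSA response endpoints** (SAP 7.4.2.2 and 7.4.2.3): stratified Cochran–Mantel–Haenszel (CMH) test, response rates with exact intervals, Mantel–Haenszel risk difference with 95% CI.
- **TTPP2** (SAP 7.4.2.1): Kaplan–Meier only, no test.

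On the significance level, SAP 7.1.1 says "All statistical comparisons will be made using two sided tests at the" 0.05 level unless stated otherwise, and SAP 7.8 states nothing otherwise. Neither document plans a treatment-by-subgroup interaction test, a homogeneity test, or a rule for reading differences between levels.

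**The concern.** Whether enzalutamide's advantage differs between types of patient is a question about the difference between subgroup levels. Separate tests within each level do not answer it. Each level holds only part of the events, so a uniform effect will often reach p<0.05 in one level and miss it in the other by chance. With 20 baseline splits and several endpoints there are many chances for such a pattern, and nothing in the plan supplies the comparison that would put it in perspective. At stake is the interpretation of exploratory results. The primary test and its type I error are not touched.

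**Working it through.** **Inputs from Protocol 7.1.** "Median TTPP1 with enzalutamide: 10.5 months"; "Median TTPP1 with flutamide: 6 months"; "Type I error of the two-sided test is 0.05, and power is 90" per cent; 1:1 allocation; 135 events. Protocol 2.2.1 sets the data cut-off at no fewer than 135 TTPP1 events.

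**Reproducing the plan's figure.** HR = 6/10.5 = 0.571, and |ln HR| = 0.5596. Schoenfeld: 4 × (1.960 + 1.2816)² / 0.5596² = 134.2, rounded up to 135. The protocol's event-probability formula gives 0.858 (enzalutamide) and 0.966 (flutamide), mean 0.912, so 135/(2 × 0.912) = 74 per group. Both stated figures reproduce.

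**Counting the splits in SAP 7.8.** There are 17 variables. Five are cut two ways (age, bicalutamide duration, PSA nadir, Week 13 response, first-line hormonal therapy duration), giving 22 splits. The two Week 13 response splits are post-baseline, which leaves 20 baseline splits. Disease stage is three-way, so 19 are two-way, and 11 of those are cut at the median.

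**Power in each half of a median split.** Assume half the events fall in each half (67.5) and the same HR in everyone.

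- Power q = Φ(√67.5 × 0.5596/2 − 1.96) = Φ(0.339) = 0.633.
- The halves hold different patients, so they are treated as independent.
- Exactly one half significant: 2 × 0.633 × 0.367 = 46.5%.
- Both: 0.633² = 40.0%. Neither: 0.367² = 13.5%.
- Expected over the 11 median splits: 11 × 0.465 = 5.1. Correlation between splits does not change an expected count.

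A patient-level simulation agrees, with 47.2%, 38.3% and 14.5% for one, both and neither. It used 6,000 trials of 200 subjects, exponential times, 12-month accrual, no dropout, cut-off at the 135th event, random halves and an unstratified log-rank test.

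**Sensitivity of the one-half-only figure.**

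| Total events | True HR | Event share | Exactly one half significant |
|---|---|---|---|
| 135 | 0.571 | 50/50 | 46.5% |
| 150 | 0.571 | 50/50 | 43.6% |
| 165 | 0.571 | 50/50 | 40.4% |
| 183 | 0.571 | 50/50 | 36.1% |
| 135 | 0.50 | 50/50 | about 30% |
| 135 | 0.45 | 50/50 | about 17% |
| 135 | 0.40 | 50/50 | about 7% |
| 135 | 0.571 | 60/40 | 48.4% |
| 135 | 0.571 | 70/30 | 53.9% |

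The 183 is 200 × 0.912 = 182.4, rounded up: all 200 subjects followed as planned with no dropout. The HRs other than 0.571 and the unequal shares are assumptions. For HR 0.50: q = Φ(√67.5 × 0.6931/2 − 1.96) = Φ(0.887) = 0.813, and 2 × 0.813 × 0.187 = 30%.

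**What an interaction test would do.** Its false-positive rate under a uniform effect is 5% per split, so 11 × 0.05 = 0.55 expected false signals over the median splits, against 5.1 one-half-only patterns. The standard error of the log ratio of hazard ratios is √(4/67.5 + 4/67.5) = 0.344. For 80% power the ratio must be exp((1.96 + 0.8416) × 0.344) = 2.6. At a ratio of 2.0, power is Φ(0.693/0.344 − 1.96) = 52%.

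**The case against.** The strongest reply is that the plan does not judge effect differences by p-values. A reader might infer that it treats a significant result in one half only as evidence of effect modification. No such rule appears in either document: the objective is to evaluate efficacy in subgroups, and it is exploratory. A reader might also infer that the plan offers nothing but tests. That is wrong too. Protocol 7.4.1.3 extends the subgroup analysis to the secondary analysis of TTPP1, so Cox hazard ratios with 95% CIs come out per level, and the PSA response endpoints bring risk differences with CIs. A careful reader can compare those. All of this stands.

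So does the point about size. The 46% applies near the design HR and at the minimum event count, and falls with more events or a stronger effect. Applying it to all 19 two-way splits, for about 9 discordant, goes beyond what the documents support: 8 of the 19 are not median splits and their event shares are unknown. Those shares could move the figure either way.

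Finally, the interaction test is weak at this sample size, and a non-significant result would be little reassurance. This is true and should be stated. It does not make within-level p-values a better guide. The gap left after these concessions is that the between-level comparison is not specified, while within-level p-values are.

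**Conclusion.** The point holds as a minor improvement to exploratory reporting. SAP 7.8 produces within-level 0.05 tests alongside useful per-level estimates, and nothing compares the effect between levels. For TTPP1 with a uniform effect, a median split would show significance in exactly one half about 46% of the time at HR 0.571 and 135 events, or about 5 of the 11 median splits. The figure is about 36% at 183 events, and about 30% at HR 0.50 with 135 events. It assumes equal events per half and the usual large-sample approximation for the log-rank statistic. No corresponding figure was derived for rPFS or PSA response, because the documents give no design assumptions for them. The findings do not bear on the primary analysis, and they do not show that the plan intends to select patients from subgroup p-values.

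**What to change.** In SAP 7.8:

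1. Keep, for each level, the counts, the hazard ratio (TTPP1, rPFS) or risk difference (PSA response), and the 95% CI.
2. Drop the within-level p-values.
3. Add one treatment-by-subgroup interaction p-value per baseline variable from the Cox model already planned, and for the CMH endpoints a test of homogeneity of the treatment effect across the subgroup levels. Where a variable has two cuts, name the one that carries the p-value. Disease stage has three levels, so its test has 2 degrees of freedom; it is omitted for rPFS.
4. Label these results exploratory and state their power: with 67.5 events per half, about 52% for a ratio of hazard ratios of 2.0, and 80% only at about 2.6.

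The cost is one extra model term per variable and a few lines of SAP text, with no new data and no change to sample size. If the SAP is no longer open to amendment, SAP section 1 already provides for justifying changes in the clinical study report. The drawback is the low power, so a non-significant interaction must not be read as proof of a uniform effect.
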